6.2.1 Management of AT13387 toxicity

Dexamethasone and/or antihistamines could be given to treat or prevent the systemic infusion reactions. Antiemetics, anti-diarrheal agents, etc. may be given to treat or prevent gastrointestinal toxicities.

6.2.1.1 Dose Reduction and Interruption

Table 6-15: AT13387 Dose Modification for Toxicities Not Specified in Subsequent Sections

CTCAE Grade	Action and Dose Modification
Grade 1	
Continue study treatment at same dose level (no dose modification).Monitor closely.Provide supportive care according to institutional standards.
Grade 2 (Tolerable)	
Interrupt study treatment if clinically indicated.Monitor closely.Provide supportive care according to institutional standards.When toxicity resolves to grade 1 or baseline, restart study treatment at current dose level.
Grade 2 (Intolerable) Grade 3	
Interrupt study treatment.Monitor closely.Provide supportive care according to institutional standards.When toxicity resolves to grade 1 or baseline, restart study treatment reduced by one dose level.If the grade 3 toxicity recurs, interrupt study treatment.When toxicity resolves to grade 1 or baseline, restart study treatment reduced by another dose level.
Grade 4	
Interrupt study treatment.Monitor closely.Provide supportive care according to institutional standards.Restart with study treatment reduced by one dose level once toxicity resolves to grade 1 or baseline.If the grade 4 toxicity recurs, either permanently discontinue study treatment or, if the patient is clinically benefiting, discuss continuation of study treatment with the CTEP Medical Monitor.
In the event of abdominal pain or suspected pancreatitis, amylase and lipase laboratory samples should be collected for confirmation of the diagnosis.	

Dose reductions for QTc elevations

A 12-lead EKG will be performed in triplicate prior to the start of each AT13387 infusion. If a subject's QTc is >480 msec but ≤ 500 msec, the infusion will be withheld until the subject's QTc has decreased to ≤ 480 msec and then the subject may be dosed at the same dose level. If a subject's QTc is ≥ 500 msec, the treatment will be withheld until the subject's QTc has decreased to <480 msec and then the subject will be dosed at one dose level below their assigned treatment.

Dose modifications for ocular toxicity

While ocular toxicity is an adverse event of special interest, dose reductions and modifications will be made based on the table above (Table 6-13). Additionally, patients will be required to

have an ophthalmology visit within 24 hours of first event of visual disturbance.

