- 3.2.9 Patients known to be HIV-positive patients and on combination antiretroviral therapy are ineligible because of the potential for pharmacokinetic interactions with the study drugs. In addition, these patients are at increased risk of lethal infections when treated with marrow-suppressive therapy. Appropriate studies will be undertaken in patients receiving combination antiretroviral therapy when indicated.
- 3.2.10 History of another malignancy other than the study indication under this trial within 5 years of study enrollment. Does not apply to subjects who underwent successful definitive resection of basal or squamous cell carcinoma of the skin, superficial bladder cancer, in situ cervical cancer, in situ breast cancer, or other in situ cancers.

Exception: Patients with history of RAS mutation-positive tumors are not eligible regardless of interval from the current study. Prospective RAS testing is not required. However, if the results of previous RAS testing are known, they must be used in assessing eligibility.

- 3.2.11 History of interstitial lung disease or pneumonitis.
- 3.2.12 History or current evidence/risk of retinal vein occlusion (RVO) or retinal pigment epithelial detachment (RPED):

- History of RVO or RPED, or predisposing factors to RVO or RPED (e.g., uncontrolled glaucoma or ocular hypertension, uncontrolled systemic disease such as hypertension, diabetes mellitus, or history of hyperviscosity or hypercoagulability syndromes).
- Visible retinal pathology as assessed by ophthalmic exam that is considered a risk factor for RVO or RPED such as evidence of new optic disc cupping, evidence of new visual field defects, and intraocular pressure >21 mm Hg.

3.2.13 History or evidence of cardiovascular risk including any of the following:

- An average of the three most recent QT intervals corrected for heart rate using the Bazett's formula QTcB ≥ 460 msec.
- History or evidence of current clinically significant uncontrolled arrhythmias (exception: patients with controlled atrial fibrillation for >30 days prior to randomization are eligible).
- History of acute coronary syndromes (including myocardial infarction and unstable angina), coronary angioplasty, or stenting within 6 months prior to randomization.
- History or evidence of current \geq Class II congestive heart failure as defined by the New York Heart Association (NYHA) functional classification system

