5. TREATMENT PLAN

5.1 Agent Administration

Treatment will be administered on an outpatient basis. A cycle of treatment will be 28 days in length. IV administration will begin approximately the same time oral agents are dosed, but not more than 10 minutes after oral agents are taken. For Cycle days 8 and 15, patients will be instructed to bring oral agents with them to be given in the clinic. Patients are asked to maintain a medication diary for recording each dose of Dabrafenib and Trametinib (Appendix D).

Reported adverse events and potential risks are described in Section 7. Appropriate dose modifications are described in Section 6. No investigational or commercial agents or therapies other than those described below may be administered with the intent to treat the patient's malignancy. The patient will be requested to maintain a medication diary of each dose of medication. The medication diary (Appendix D) and pill bottles will be returned to clinic staff at the end of each course. To document compliance, a pill count will be performed of all unused pills.

Dosing levels for the study are listed below in Table 5.1. Dose level 1 will be the first dose level. Intrapatient dose escalation will be allowed when safe and feasible once the next higher dose level has been cleared. Additional, intermediate dose levels may be enrolled under the following

conditions:

- 1) Toxicity is seen at a dose level where dose modification is necessary and the prior, lower dose level was treated without DLT or analysis of the PK data suggests that an intermediate dose would be appropriate;
- 2) An intermediate dose is conceivable based on the size of pills and nature of the toxicity at the higher dose;
- 3) Consensus agreement is made between investigators, industry sponsors, and CTEP;
- 4) CTEP and IRB approval of an amendment to the protocol that clearly describes the rationale for and the logistics of the intermediate dose level.

Table 5.1 Dose Escalation Levels for Phase I Study

Dose Level	Dabrafenib [BID/PO]	Trametinib [QD/PO]	AT13387 [D1,8,15/IV]
-1	75 mg	1 mg	180 mg/m ²
1	150 mg	1 mg	180 mg/m ²
2	150 mg	2 mg	180 mg/m ²
3	150 mg	2 mg	220 mg/m ²
4	150 mg	2 mg	260 mg/m ²

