6.1.12 Dabrafenib or Dabrafenib + Trametinib Dose Modification for QTc Prolongation

Table 6-8: Dabrafenib + Trametinib modification for QTc Prolongation

Prolongation	Action and Dose Modification
• QTcB \geq 501 msec	
 Interrupt study treatment until QTcB prolongation resolves to grade 1 or baseline. Test serum potassium, calcium, phosphorus and magnesium. If abnormal, correct per routine clinical practice to within normal limits. Review concomitant medication usage for agents that prolonged QTc. If the event resolves, restart study treatment at current dose level.^b If the event does not resolve, permanently discontinue study treatment. Consider evaluation with cardiologist. If the event recurs, permanently discontinue study treatment. Consider evaluation with cardiologist.

Abbreviations: msec = milliseconds; QTcB = QT interval on electrocardiogram corrected using the Bazett's formula
 a. Based on average QTc value of triplicate ECGs. For example, if an ECG demonstrates a prolonged QT interval, obtain two or more ECGs over a brief period, and then use the averaged QTc values of the three ECGs to determine if study treatments should be interrupted or discontinued.
 b. If the QTc prolongation resolves to grade 1 or baseline, the subject may resume study treatment if the investigator and CTEP medical monitor agree that the subject will benefit from further treatment.

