6.2 AT13387 Dose modifications

AT13387 dosing may be reduced in the setting of toxicity. The below table denotes the possible dose levels based on the dose escalation schema.

Current Dose	If Dose Reduction Required	Reduce To
260 mg/m ² days 1, 8, and 15	→	220 mg/m ² days 1, 8, and 15
220 mg/m ² days 1, 8, and 15	→	180 mg/m ² days 1, 8, and 15
180 mg/m ² days 1, 8, and 15	→	150 mg/m ² days 1, 8, and 15
150 mg/m ² days 1, 8, and 15	→	Discontinue AT13387

Further dose modifications to 120 mg days 1, 8, and 15 are permitted at the discretion of the Investigator but should be discussed with CTEP and the study sponsors. In the event that dabrafenib, trametinib, or both agents need to be discontinued due to toxicity reasons, treatment with AT13387 may continue at the discretion of the investigator until time of disease progression.

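### Section 6.2.1.1: a pre-infusion QTc of exactly 500 msec falls in both AT13387 bands, and the text does not say which one governs

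*Combined protocol and SAP*

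**What the plan says.** Section 6.2.1.1 requires a triplicate 12-lead EKG before every AT13387 infusion and then gives two rules.

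- **Lower band.** If the "QTc is >480 msec but ≤ 500 msec, the infusion will be withheld until" it has come down to 480 msec or less, "and then the subject may be dosed at the same dose level".
- **Upper band.** If the "QTc is ≥ 500 msec, the treatment will be withheld until" it has come down to below 480 msec, "and then the subject will be dosed at one dose level below their assigned treatment".

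The size of one step comes from Section 6.2, which introduces its table with "The below table denotes the possible dose levels based on the dose escalation schema". The steps are 260 to 220, 220 to 180, 180 to 150 mg/m², and 150 to discontinuation. A further 120 mg option is left to investigator discretion, to be discussed with CTEP and the study sponsors. The starting doses are in Section 5.1, "Table 5.1 Dose Escalation Levels for Phase I Study": 180 mg/m² at levels -1, 1 and 2, 220 at level 3 and 260 at level 4.

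The partner drugs have a separate QTc rule in Section 6.1.12, Table 6-8, "Dabrafenib + Trametinib modification for QTc Prolongation". It acts from a QTcB of 501 msec.

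**The concern.** The lower band includes 500 msec as its upper limit, and the upper band includes 500 msec as its lower limit. A patient with that reading is covered by two instructions that differ in what follows the hold. One permits the same dose; the other requires a lower one.

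This is a dose decision made before each infusion, so the wording should give a single answer for every possible reading. Section 2.2.3.4 reports QT prolongation among the serious adverse events of AT13387, and Section 7.1.1.3 lists it as possibly related to the agent. What is at stake is that a site acting on the first sentence alone could restart at full dose in a patient for whom the second sentence requires a reduction.

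**Working it through.** The check is one of logic. The plan states no figure for this point that could be reproduced.

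**Step 1: overlap of the bands.** The lower band is the interval (480, 500] and the upper band is [500, ∞). Their intersection is {500}, a single value.

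**Step 2: what each rule requires at 500 msec.**

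| | Lower band | Upper band |
|---|---|---|
| Immediate action | Withhold | Withhold |
| Release threshold | ≤480 msec | <480 msec |
| Dose on restart | Same level, permitted | One level lower, required |

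The immediate action is the same. The restart dose differs. The release thresholds differ only if the follow-up QTc is exactly 480 msec.

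**Step 3: size of the dose difference.** The difference is (assigned dose − next step) / assigned dose. Assigned doses are from Table 5.1 and steps are from the table in Section 6.2.

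- Levels -1, 1 and 2: (180 − 150)/180 = 30/180 = 16.7%
- Level 3: (220 − 180)/220 = 40/220 = 18.2%
- Level 4: (260 − 220)/260 = 40/260 = 15.4%
- Already reduced to 150 mg/m²: the next step in the table is discontinuation.

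**Step 4: search for a rule that settles it.**

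- Table 6-15, in the same section, covers toxicities not dealt with later. QTc is dealt with directly below it.
- Table 6-8 starts at 501 msec and sits in the dabrafenib and trametinib section.
- Section 5.3.3 advises caution with QTc-prolonging medication and sets no dosing threshold.
- Study calendar footnote f (Section 10) repeats the triplicate EKG before each infusion and sets no threshold.

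None of these says which band holds 500 msec.

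**Step 5: effect of the change.** With a lower band of (480, 500) and an upper band of [500, ∞), the intersection is empty. Every QTc above 480 msec then leads to one action and one release threshold. The same is true of (480, 500] with (500, ∞).

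**The case against.** The best counter-argument is that the text already gives one answer. The first sentence only permits the same dose, while the second requires a reduction, so reducing complies with both and restarting at full dose breaks the second. A site would have to overlook the very next sentence to go wrong. This argument largely stands. A reader might infer that the plan offers two equally valid doses at 500 msec; the wording does not support that. What remains is that the precedence rests on the difference between a permissive and a mandatory verb. Dosing instructions should not depend on that.

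A second argument is that Table 6-8's 501 msec cut-off shows the upper AT13387 band was meant to start above 500. That is possible, and for whole-msec readings it would align the two rules. But Table 6-8 governs other drugs, and nothing in the document states the intent. Either way, one sign in Section 6.2.1.1 is wrong.

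A third argument is that the case will hardly ever arise. Few patients are likely to be affected: Section 3.2.13 excludes at entry anyone whose QTcB is 460 msec or more, on "An average of the three most recent QT intervals corrected for heart rate using" the Bazett formula. A reader might try to derive a frequency from the two QT serious adverse events among 87 earlier AT13387 subjects in Section 2.2.3.4. That count does not measure readings of 500 msec. Section 6.2.1.1 also does not say how the triplicate EKGs are combined, so the document supports no frequency. The rarity argument limits the importance of the point but does not make the wording right.

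**Conclusion.** The wording is wrong as it stands, and the point is minor. At exactly 500 msec the two bands overlap and differ on restart dose (one step, 15.4% to 18.2% of the assigned dose, or discontinuation from 150 mg/m²) and on release threshold. A reduction is the only course that satisfies both sentences, but this has to be inferred.

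A reader might infer that the overlap could alter DLT counts, dose escalation or the MTD. The documents do not support that. Both bands withhold the infusion first, and the DLT definition in Section 5.2 refers to a missed AT13387 dose, not to the level at which dosing restarts. No sample size, interval or other statistical figure changes.

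Two assumptions apply. One level is taken to be one step in the AT13387 table of Section 6.2, and for a patient already reduced the step is counted from the current dose.

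**What to change.** In Section 6.2.1.1, change the lower band to >480 msec but <500 msec. A reading of 500 msec then takes the mandatory reduction and the <480 msec release threshold. Leave the upper band and Table 6-8 as they are.

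The sponsor should confirm the intent. If the aim was to match Table 6-8, changing the upper band to >500 msec also makes the bands exclusive, but it would permit a full-dose restart at 500 msec and is the less cautious choice.

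Either edit is one inequality sign and could go into the next amendment. It adds no procedure and changes no analysis.

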Grade 1	
 Consult ophthalmologist immediately. 	
 If dilated fundus examination cannot be performed within 7 days of onset, hold trametinib until RPED and RVO can be excluded by retina specialist/ophthalmologist. Dabrafenib may be continued. If RPED and RVO excluded, continue (or restart) trametinib at same dose level If Uveitis/Iritis, refer to table below for Iritis/Uveitis If RPED suspected or diagnosed, refer to RPED dose modification table below; report as SAE if diagnosed. If RVO suspected or diagnosed: Permanently discontinue trametinib and report as SAE if diagnosed.

CTCAE Grade	Management Guideline	Action and Dose Modification
Grade 2 and 3	
 Consult ophthalmologist immediately. 	
 Hold trametinib. Dabrafenib may be continued. If RPED and RVO excluded, restart trametinib at same dose level If Uveitis/Iritis, refer to table below for Uveitis/Iritis If RPED diagnosed, see RPED dose modification table below; report as SAE. If RVO diagnosed: Permanently discontinue trametinib and report as SAE.
Grade 4	
 Consult ophthalmologist immediately. 	
 Interrupt trametinib. Dabrafenib may be continued. If RPED and RVO excluded, may consider restarting trametinib at same or reduced dose after discussion with study medical monitor. If Uveitis/Iritis, refer to table below If RVO or RPED diagnosed, permanently discontinue trametinib and report as SAE.

Abbreviations: RPED = retinal pigment epithelial detachments; RVO = retinal vein occlusion; SAE = serious adverse event
 *If visual changes are clearly unrelated to study treatment (e.g., allergic conjunctivitis), monitor closely but ophthalmic examination is not required

Table 6-11: Dose Modification for RPED

Event CTCAE Grade	Action and Dose Modification
Grade 1 RPED (Asymptomatic; clinical or diagnostic observations only)	
 Continue trametinib with retinal evaluation monthly until resolution. If RPED worsens, follow instructions below. Dabrafenib treatment is not affected

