6.1.15 Dabrafenib + Trametinib Dose Modification for Pneumonitis

Pneumonitis has been observed in patients receiving trametinib in combination with dabrafenib. To reduce the risk of pneumonitis, patients will be monitored closely for symptoms, evaluated with imaging and functional tests when appropriate.

Table 6-13: Dabrafenib-Trametinib Treatment Modification for Pneumonitis

CTCAE Grade	Adverse Event Management	Action and Dose Modification
Grade 1	
 CT scan (high-resolution with lung windows) recommended. Clinical evaluation and laboratory work-up for infection. Monitoring of oxygenation via pulse-oximetry recommended. Consultation with pulmonologist recommended. 	Continue study treatment at current dose
Grade 2	
 CT scan (high-resolution with lung windows). Clinical evaluation and laboratory work-up for infection. Consult pulmonologist. Pulmonary function tests: If $<$ normal, repeat every 8 weeks until \geq normal. Bronchoscopy with biopsy and/or BAL recommended Symptomatic therapy including corticosteroids if clinically indicated. 	
 Interrupt trametinib until recovery to grade ≤ 1. Restart with trametinib reduced by one dose level. Escalation to previous dose level after 4 weeks and consultation with the CTEP Medical Monitor may be considered. If no recovery to grade ≤ 1 within 4 weeks, permanently discontinue trametinib.
Grade 3	
 Same as grade 2 	
 Interrupt study treatment until recovery to grade ≤ 1. Resumption of trametinib at one dose level reduction may be considered after consultation with the CTEP Medical Monitor If no recovery to grade ≤ 1 within 4 weeks, permanently discontinue trametinib.
Grade 4	
 Same as grade 2 	Permanently discontinue trametinib.

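### Section 6.2.1.1 ties AT13387 dose changes for ocular toxicity to Table 6-13, which is the pneumonitis table; context points to Table 6-15

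*Combined protocol and SAP*

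**What the plan says.** Section 6.2 covers AT13387 dose changes. It opens with an unnumbered ladder of dose levels, introduced by "The below table denotes the possible dose levels based on the dose escalation schema". Section 6.2.1.1 then gives the rules by grade under the caption "Table 6-15: AT13387 Dose Modification for Toxicities Not Specified in Subsequent Sections". After a paragraph on QTc comes a short paragraph on ocular toxicity. It calls ocular toxicity an adverse event of special interest, states that "dose reductions and modifications will be made based on the table above (Table 6-13", and requires an ophthalmology visit within 24 hours of the first visual disturbance.

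The table with the printed number is in Section 6.1.15 and is captioned "Table 6-13: Dabrafenib-Trametinib Treatment Modification for Pneumonitis". Visual changes attributed to the other two drugs have their own rules in Section 6.1.14: Table 6-10 for visual changes in general, Table 6-11 for retinal pigment epithelial detachment (RPED), and Table 6-12 for uveitis and iritis.

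**The concern.** The ocular sentence gives two pointers that disagree. The position it describes leads to Table 6-15; the number leads to a lung-toxicity table for two other drugs.

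The reference has work to do. Table 6-15 is captioned for toxicities that later sections do not cover, and ocular toxicity has its own paragraph after it. This cross-reference is what brings ocular events under Table 6-15.

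The toxicity is also one that the plan takes seriously. The text following the dose-level schema says the 1 mg trametinib starting dose was chosen because the eye effects of trametinib and AT13387 might overlap. Section 2.2.3.4 reports visual symptoms in about half of subjects on 150 or 180 mg/m2 weekly and in 5 of 7 (71%) on 220 mg/m2 weekly. Sites are therefore likely to consult this rule. At stake is whether someone who follows the number is told to hold and reduce AT13387 when the grade calls for it.

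**Working it through.** The plan states no figure to reproduce. The check sets the two tables side by side and then reads the dose steps from the ladder.

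**1. What each table does, by grade**

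| Grade | Table 6-13 (pneumonitis, Section 6.1.15) | Table 6-15 (AT13387, Section 6.2.1.1) |
|---|---|---|
| 1 | Study treatment continues at the current dose | Continues at the same dose |
| 2, tolerable | Trametinib held; "Restart with trametinib reduced by one dose level"; nothing on AT13387 | Held if clinically indicated; restarts at the current dose |
| 2, intolerable | As above; the table does not split Grade 2 | Held; restarts one level lower |
| 3 | Study treatment held until Grade 1 or better; "Resumption of trametinib at one dose level reduction may be considered after consultation with the CTEP Medical Monitor"; no AT13387 restart dose | Held; restarts one level lower |
| 4 | Trametinib stopped for good; nothing on AT13387 | Held; restarts one level lower |

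The tables agree at Grade 1. At Grade 3, Table 6-13 interrupts study treatment, which can be read to include AT13387, but it gives no AT13387 restart dose. At Grades 2 and 4 it says nothing about AT13387.

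**2. What the AT13387 step would be**

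Starting doses come from Table 5.1 and reductions from the Section 6.2 ladder.

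- Dose level 4: 260 to 220 mg/m2, 40/260 = 15.4% lower
- Dose level 3: 220 to 180 mg/m2, 40/220 = 18.2% lower
- Dose levels 2, 1 and -1: 180 to 150 mg/m2, 30/180 = 16.7% lower

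These figures describe the rule that appears to be intended. They do not measure harm from the misprint.

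**3. Which table was meant**

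Table 6-15 is in the same subsection, above the sentence. It is the only numbered table in Section 6.2 and the only one that gives AT13387 actions by grade. Table 6-10 is on topic, but it sits in Section 6.1 and its actions concern trametinib and dabrafenib. The ladder has steps but no grades to trigger them. This leaves Table 6-15.

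**4. How often it could matter**

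Section 2.2.3.4 describes AT13387 visual symptoms as generally Grade 1, transient and reversible. In its adverse event table, Grade 3 or 4 events number 0 of 86 for visual impairment and 1 of 86 for a further row whose label begins with the word Vision and is cut off. No separate Grade 2 count is given for AT13387 visual events. Section 2.2.1.3 reports eight Grade 2 RPED cases among about 1,600 trametinib patients, which is a different drug and a single diagnosis. The number of patients in this trial who might meet the affected rows cannot be worked out from the documents, but at Grades 3 and 4 the AT13387 data suggest few.

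**The case against.** The best reply is that the text corrects itself. The sentence sits in the AT13387 section and points upward to the only graded AT13387 table there. A reader who turns to Table 6-13 meets lung CT, pulmonology and bronchoscopy and will see at once that it is the wrong place. Section 6 also opens by saying that every agent is modified when the responsible one is hard to determine. Most of this stands, and it is why the point is minor. It does not make the number right: Table 6-13 also lies earlier in the document, and a table number is the more specific of the two pointers.

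A reader might infer a trametinib conflict. With RPED and retinal vein occlusion (RVO) excluded, Table 6-10 says for Grades 2 and 3 "If RPED and RVO excluded, restart trametinib at same dose level", and for Grade 4 that the site "may consider restarting trametinib at same or reduced dose after discussion with study medical monitor", whereas Table 6-13 reduces or stops trametinib. The documents do not support this as a conflict in the plan. The ocular paragraph belongs to the AT13387 section, and trametinib for visual changes is governed by Tables 6-10 and 6-11, which the misprint leaves untouched. Misdosing trametinib this way would mean using an AT13387 paragraph and a pneumonitis table while ignoring the dedicated visual-change rules.

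A reader might also infer an effect on DLT counts, because Section 5.2 defines an intolerable event partly by a missed AT13387 dose in cycle 1. The documents do not show one. DLT status is set by Section 5.2 from grade, relatedness and tolerability. Nothing indicates that any site would hold or give a dose because of the misprinted number.

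**Conclusion.** The cross-reference is wrong as printed, and the fault is a minor one of safety text. A rule for AT13387 and ocular toxicity exists and can be found, so nothing is missing from the plan. The exposure is limited to a reader who trusts the number over the position, and to Grade 2 and above. For that reader, Table 6-13 gives no AT13387 restart dose at any of those grades and no instruction to hold AT13387 at Grades 2 and 4. No effect on escalation, sample size or analysis is shown.

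Two assumptions support this. That Table 6-15 was intended is an inference, though a strong one. That Table 6-13 interrupts AT13387 at Grade 3 depends on reading study treatment to cover all three drugs.

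**What to change.** In the ocular toxicity paragraph of Section 6.2.1.1, replace Table 6-13 with Table 6-15. The cost is one table number, with no change to design, sample size, data collection or analysis.
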